1. *Summarize the research design and sequentially identify all procedures to be performed to accomplish the specific aims of the project. Clearly identify and distinguish procedures that are considered experimental, procedures that are performed exclusively for research purposes (including "extra" routine tests), and procedures that would occur regardless of the research (i.e., standard of care). Point out any procedures, situations, or materials that may be hazardous, and the precautions to be exercised to maintain subject safety:* 1. Clinic schedules for the medical providers on the research team will be reviewed in advance and any patient that is under the age of 20 and receiving depot-medroxyprogesterone will be contacted by telephone in advance to offer participation in the project. 2. The telephone call will follow the attached script. Two attempts will be made to call patients. 3. If subject is interested in participating, a prescription for the subcutaneous version of depot-medroxyprogesterone will be sent to their pharmacy to be picked up by the subject prior to the office visit. 4. Subjects under 18 will be instructed that they must be accompanied by a parent or guardian. At the office visit, written consent/assent will be obtained. 5. Subject will be shown the instructional video, which is approximately 3 minutes long (video submitted in attached word document with a link, Consent on file for actor in video). They may view as many times as they want. 6. Once ready, the healthcare provider from the research team will observe, without giving verbal instruction, the patient give themselves a subcutaneous depot-medroxyprogesterone injection. 7. If at any point the provider feels that the subject is not performing the injection safely or correctly the healthcare provider will intervene to ensure that the medication is given correctly, and this will be recorded within the REDCap survey. 8. After the injection is given, the subject will fill out the REDCap survey and study team member administering injection will input observational data into REDCap. 9. Subject will be asked to repeat another questionnaire in REDCap at the time of the next injection which will be scheduled for 12 weeks later. The next visit is as per standard of care scheduling (this medication is routinely administered at approximately 12 week intervals). If the subject comes into the same office for the injection, the survey will be filled out in person. If the subject does not come in to the same office, a link to the follow up REDCap survey will be emailed to the subject with instructions on how to access the survey. Email addresses will be confirmed at the time of the first visit, as is routine for medical care.

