Data and specimens should be stored in a secure location only accessible by the research team. The PI must ensure that study documents are stored in a manner that protects the privacy of subjects and the confidentiality of study data.

1. *State where the study records, both electronic and/or paper documents including signed ICFs/assent forms, will be retained during the study (state the location for original document plus any copies that are made, e.g., if a copy of the ICF will be retained in the subject's medical record):* A key containing the link between coded REDcap responses and patient names will be kept separately in a password protected HIPAA compliant Box account set up through Tufts Medical Center. The REDCap does not collect any identifiers and each subject will have a unique sequential code attached to their survey. This will only be accessed by the study team and will be destroyed at the completion of the study. The Key and any downloaded REDCap coded data will have two different passwords. Paper consent forms will be stored in a folder in a locked cabinet in a locked office that will only be accessible by [name] and [name] (PI).

2. *State where study records will be retained when the study has been closed (long-term storage):* The paper consent forms will be stored in the locked cabinet in the locked office following Tufts data retention policies. Identifiable data that is entered into the HIPAA compliant Box account will not be stored long term and will not be accessed by anyone other than the research team. Data will be destroyed at the culmination of the study.
3. *State who, in addition to the research team, will have access to the study files, data, and/or specimens:* Only [name] and [name] will have access to the consent forms. Study files in Box will be accessed only by the research study team for the duration of the study. Nobody other than the research team will have access to this data.
4. *Will data (or specimens) be sent outside of Tufts Medical Center or Tufts University and/or sent between Tufts Medical Center and Tufts University?*

Yes No

If Yes, respond to all of the following:

 - a. *Describe the nature of the data/specimens to be transferred:*
 - b. *State to whom or what entity the data/specimens will be transferred:*

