1. *Describe the primary and secondary study endpoints:* The primary outcome for this study is successful or not successful (i.e., 1/0) self administration of depot-medroxyprogesterone by study participants. A secondary outcome is understanding whether or not study participants will continue to use self administered injections in the future. In addition to these quantifiable outcomes, the study will also collect feasibility information, such as ease of identifying eligible study participants, potential participants willingness to consent, or participants willingness to pick up the prescribed medication prior to an in-person appointment.
2. *Describe any primary or secondary safety endpoints:*

I.2 Sample Size Justification Statistical Analyses

1. *Describe the statistical analyses that will be performed for this study:* This is a pilot study, designed to understand the feasibility of larger scale studies, including those with a comparison group, in the future. Key questions include the statistical properties of the dependent variables, including response rates for survey items and the injection success rate. The analysis will be descriptive, looking at the completeness of the survey data, correlation among survey items, and the injection success rate (to help inform future power analysis, among other things). We will also assess concordance between the observing physician and the patient on the success of the injection using a kappa statistic. Finally, we will compare injection success based a patient's assessment of willingness to continue using self injection in the future. After the initial survey, a

second survey will be given to participants approximately 12 weeks later, to see if participants self inject a second time.

2. *Provide a sample size justification:* Since this is a treatment group-only pilot study, formal power analysis was not conducted. We are targeting 30 participants to better understand how many teenagers complete all steps in the study process (i.e., meet study criteria, consent, pick up medication, attend appointment, attempt injection, complete surveys). The team will make efforts to understand study drop-out at each stage. We also want to better understand the relationship between key covariates, such as convinence of home injection, and the outcome.

I.3 Number of Subjects

1. *Specify the number of subjects to be enrolled in total across all sites:* or N/A this is not a multicenter study.

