2. *Specify the number of subjects to be enrolled at the Tufts site. Subjects who sign an ICF are considered "enrolled". For studies that have a separate screening ICF, this number is the number of subjects who sign a screening ICF:* 50
 - a. *Provide the rationale for enrolling this number of subjects at the Tufts site: it is anticipated that 50 will need to be enrolled to achieve 30 to complete the study*
 - b. *Estimate the number of subjects expected to be enrolled at the Tufts site (i.e. sign the screening or study ICF) as well as the number needed to complete the study at the Tufts site: 50 enrolled, 30 complete*
 - c. *If a large number of withdrawals and/or dropouts is expected, explain why: not expected*

I.4 Data Management

1. *Describe the data analysis plan, including descriptions of the data:*

The data are survey results, collected and stored in the Tufts instance of RedCAP. Each encounter will result in two surveys: one from the patient and one from the clinician. Each survey will have a unique identifier for the provider and an encrypted identifier for the patient.

Descriptive analysis will start with data completeness. Next, we will look at the frequency of all variables, including the patient's self-assessment of a complete injection with the provider's assessment of the injection. We will look at the correlation between self-perception of a successful injection and age, assessment of the video and self-reported intent to do self-injection in the future. We will also assess the degree to which patients and providers agree on the quality of the injection (kappa statistics to assess concordance on injection success).

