2. *Describe the steps that will be taken to secure the data (e.g., training, authorization of access, password protection, encryption, physical controls, certificates of confidentiality, and separation of identifiers and data) during storage, use, and transmission:* All data entered into REDCap will be coded. Subjects will be given numbers by the REDCap survey, and these numbers will be assigned in the sequential order the subjects complete the surveys. These numbers will be linked to their names, and the key will be kept in a password protected online file in a HIPAA secure Box file created by Tufts Medical Center. Only research team members will have access to this file. The file will be destroyed at the end of the study. Consent forms will be kept in a locked cabinet in a locked office accessible only by [name] and [name].
3. *Describe any procedures that will be used for quality control of collected data:* One challenge with data collection is making sure the provider survey and patient survey are correctly linked. To test this, the team will review a random 5 cases and make sure the date, time and provider match. During the analysis, we will see if any surveys are incomplete. If yes, we'll seek to understand any patterns. For example, are teens in a specific age group leaving items blank? Are patients seen at a particular time of day or by a specific clinician skipping items. This type of information will be used to decide if incomplete surveys can be used in the analysis.

To ensure data integrity, downloads from RedCAP will be dated and carefully managed to make sure incomplete data sets are not used for analysis. Only members of the study team will have access to the analytic file and results will be reviewed by multiple team members. All final tables will clearly show the number of cases involved in the analysis and identify the analytic data set used to generate results.

4. *Describe how data and specimens will be handled study-wide as follows:*
 - a. *What information will be included in that data or associated with the specimens:* Each survey will be given a number by REDCap, and this number will be recorded and linked to the patient's name. The key that has the names and numbers will be stored in a HIPAA compliant password protected Box account for the PI and only research team members will have access to this Box account.

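### Minor, cheap improvement: the five-case check of patient–provider survey linkage would probably miss an isolated swap, and checking all 30 to 50 pairs costs little

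*Protocol*

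**What the plan says.** Section I.4, item 3 of the protocol names the risk itself: "One challenge with data collection is making sure the provider survey and patient survey are correctly linked". The only test it sets for that risk is that "the team will review a random 5 cases and make sure the date, time and provider match". It does not say what follows if one of the five fails.

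Two planned analyses depend on the pairing:
- Section I.2, item 1: "We will also assess concordance between the observing physician and the patient on the success of the injection using a kappa statistic". Section I.4, item 1 repeats this ("kappa statistics to assess concordance on injection success").
- Section I.2, item 1 also says that "we will compare injection success based a patient's assessment of willingness to continue using self injection in the future". This needs the pairing if success is taken from the provider's form.

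The protocol also has controls that make mislinkage less likely:
- Both forms are completed at the same visit. Section F.2, step 8 says that "the subject will fill out the REDCap survey and study team member administering injection will input observational data into REDCap".
- Section G.4, item 1 says that "each subject will have a unique sequential code attached to their survey", and item 6 has the key carry the matching number.
- Section I.4, item 1: "Each survey will have a unique identifier for the provider and an encrypted identifier for the patient".

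**The concern.** A spot check of a few records is good at finding a fault that affects many of them and poor at finding one that affects two. An isolated swap, with one patient's form joined to another patient's provider form, is of the second kind. The coding and same-visit procedures reduce the chance of a swap, but they do not verify that the finished pairs are right. The five-case review is the only stated step that does.

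At stake is the kappa, which depends wholly on correct pairing, and possibly the comparison of success by willingness to continue. A linkage error would not show in a confidence interval and would, on average, lower the apparent agreement. It also becomes hard to repair once the key linking numbers to names is gone. Section I.4, item 4c has the key destroyed when the study and data analysis are complete. Section B.2, item 1 reads as if this happens earlier, once the surveys are completed.

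**Working it through.** The protocol gives no detection probability for this check, so there is no figure of its own to reproduce.

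**Inputs from the protocol**
- Cases reviewed: n = 5 (section I.4, item 3).
- Number of pairs: N between 30 (completing) and 50 (enrolled) (section I.3, item 2).

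**Assumptions**
- One swap makes two cases wrong, so m = 2.
- Any mislinked case that is reviewed is recognised. This favours the protocol: two patients of one provider on one day would differ only by time.

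**Probability that five cases miss one swap:** C(N−2, 5) / C(N, 5) = (N−5)(N−6) / [N(N−1)]
- N = 30: (25 × 24)/(30 × 29) = 600/870 = 0.690
- N = 50: (45 × 44)/(50 × 49) = 1980/2450 = 0.808

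With two swaps (m = 4) the miss probabilities are 0.46 and 0.65.

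**Detection of a systematic fault (half the records shifted):** 1 − C(N/2, 5)/C(N, 5)
- N = 30: 0.979
- N = 50: 0.975

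**Sample needed to detect one swap with at least 95% probability**
- N = 30: 23 cases, since 1 − (7 × 6)/870 = 0.952
- N = 50: 39 cases, since 1 − (11 × 10)/2450 = 0.955

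A sample that size is close to a full check.

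**Effect of one swap on kappa.** The agreement tables are assumptions, because the protocol gives none. Each is written as both success / patient-only success / provider-only success / both failure. All C(30, 2) = 435 exchanges of provider ratings were enumerated at N = 30.

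| Table | Kappa | Swaps with no effect | Size of change otherwise | Mean change |
|---|---|---|---|---|
| 27/0/0/3 | 1.00 | 354 (81%) | 0.370 | −0.069 |
| 24/0/0/6 | 1.00 | 291 (67%) | 0.208 | −0.069 |
| 21/0/0/9 | 1.00 | 246 (57%) | 0.159 | −0.069 |
| 26/1/1/2 | 0.63 | 382 (88%) | 0.370 | −0.043 |
| 22/2/2/4 | 0.58 | 343 (79%) | 0.208 | −0.040 |
| 18/3/2/7 | 0.62 | 303 (70%) | 0.154 | −0.042 |

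Worked example for 27/0/0/3. Only an exchange between a success and a failure matters, which is 27 × 3 = 81 of 435. It gives 26/1/1/2, with observed agreement 28/30 = 0.933 and chance agreement (27² + 3²)/900 = 0.82. Kappa is then (0.933 − 0.82)/0.18 = 0.63, a change of −0.370. The mean over all swaps is −0.370 × 81/435 = −0.069.

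Multiplying the mean change by the miss probability of 0.690 gives −0.03 to −0.05 at N = 30. At N = 50 the mean change is −0.041 from perfect agreement and −0.023 to −0.026 from kappa of about 0.6. Multiplied by 0.808, that is about −0.02 to −0.03.

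For scale, the large-sample standard error of kappa in the three N = 30 tables near 0.6 is 0.24, 0.19 and 0.15.

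**The case against.** The strongest reply is that this is a preference about the size of a spot check. The five cases test whether linking works, and for a systematic fault they do that well. The protocol does not claim that they exclude every error, and nothing in it bars a wider look if one case fails. The kappa is one descriptive item in a pilot with no formal power analysis, is not among the endpoints in section I.1, and drives no decision.

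There are further safeguards. Incorrect self-administration is also written in the medical record (section H.2, item 1). The same small team observes the injection, sees that the patient's survey is completed and fills in its own (section K.3, item 1). Several team members review the results (section I.4, item 3).

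Most of this stands, and it keeps the point minor. It does not remove the point, because none of these safeguards verifies a pair. The protocol itself singled out linkage as a difficulty and then fixed the number of cases, so this is a stated rule and not a detail left open.

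Three stronger readings are not supported:
- A reader might take 0.69 to 0.81 as a risk that the data are mislinked. It is the chance of missing a swap given that one occurred, and the protocol gives no rate of occurrence.
- A reader might infer that the main result is at risk. The success rate, the correlations within one survey and the feasibility counts do not use the pairing.
- A reader might fault the check for leaving out the encrypted patient identifier. If that identifier is the linking field, which is likely though not spelled out, every pair agrees on it by construction, even when a form was entered under the wrong code. Date, time and provider are then the informative fields, and the protocol already uses them.

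**Conclusion.** The point holds as a minor improvement. As a test for an isolated swap the stated check is weak, missing it with probability 0.69 (30 pairs) to 0.81 (50 pairs). As a test for a large systematic fault it is adequate, at about 0.97 to 0.98.

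The expected consequence is small. Depending on the assumed table, 57% to 88% of single swaps at N = 30 leave kappa unchanged, and the mean change is well below kappa's own sampling error. The swaps that do matter, 12% to 43% of them, move kappa by 0.15 to 0.37, which is as large as that sampling error or larger.

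The miss probabilities follow from the protocol's numbers and the two assumptions above. The kappa figures rest on assumed agreement tables. The case for a change is only that the remedy costs so little.

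**What to change.** In section I.4, item 3, replace the five-case sample with a check of every patient–provider pair on date, time and provider. Do it before analysis and before the key is destroyed, and resolve any mismatch against the key and the medical record. Because sections B.2 and I.4 place the destruction of the key at different times, the simplest course is to check pairs as the surveys come in.

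This takes the sampling miss probability from 0.69–0.81 to zero. A swap that does not show in date, time or provider could still escape. The cost is one change of wording and perhaps an hour or two for 30 to 50 pairs (an assumption), with no new data, form or visit.
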